Improving Weight Loss Outcomes for Binge Eating Disorder
Statistical Analysis Plan
NCT03712462
March 18, 2024

Statistical Analysis Plan

Statistical analyses were completed using R software version 4.1.3. Data were imputed via two methods to address missingness. Single imputation was used to impute weight measurements using a return-to-baseline approach, with dropouts assumed to have regained 0.15lb per week up to their baseline weight, consistent with assumptions used by other weight loss clinical trials (Wing et al., 2006). Other missing variables were imputed using R “mice” package (Van Buuren & Groothuis-Oudshoorn, 2011). Descriptive statistics were generated for all variables at each assessment point by treatment condition. There were no differences in age, sex, racial or ethnic status, and therapist credentials between treatment conditions.

Mixed effects models were conducted for Primary Aim 1 (Efficacy of ABT) and Secondary Aim 2 (Between-Subjects Moderation) given nested data within subjects and group. The R “merTools” package was used for models predicting percent weight change and global eating disorder psychopathology change (Knowles et al., 2023), and the R “cplm” package was used for models predicting binge eating frequency change (due to zero-inflated distribution of percent binge eating change at post-treatment and follow-up) (Zhang, 2013). Models for percent weight and binge eating change included fixed effects for the interaction between linear or quadratic time effects and treatment condition (and baseline moderators for Secondary Aim 2). Only linear time effects were included in the models for global eating disorder psychopathology, since the quadratic time fixed effect did not significantly improve model fit. Model selection criteria (e.g., Aikaike information criteria, Bayesian information criteria) and significance testing were used to identify the random effects structure that best fit the model. For percent weight change, models included separate random effects for intercept and slopes of quadratic time effects nested within subjects. For binge eating frequency change, models included random effects for intercept nested within subjects. For global eating disorder psychopathology change, models included separate random effects for intercept and slopes of linear time effects nested within subjects. No differences in results were observed when treatment format delivery (i.e., telehealth vs. in-person groups) was included as a covariate; therefore, results without the inclusion of treatment format delivery as a covariate are reported. Statistically significant interactions were interpreted by plotting simple regression lines for each variable. For all linear mixed effects models, alpha was set at 0.05 and confidence intervals were obtained. Cohen’s f^2 effect size measures were estimated for group x time interaction using methods described by Selya and colleagues (Selya et al., 2012), with $f^2 \geq 0.02$, $f^2 \geq 0.15$, and $f^2 \geq 0.35$ representing small, medium, and large effect sizes, respectively.

For Secondary Aim 1, mediation analyses were conducted using the R “lavaan” structural equation modeling package (Rosseel, 2012). Mediation analyses estimated the indirect effect of treatment condition through change in each mediator from baseline to 3-months on percent change in weight, binge eating frequency change, and global eating disorder psychopathology change at post-treatment and through changes from baseline to 6-months on weight, binge eating frequency change, and global eating disorder psychopathology change at one year follow-up. Baseline levels of the dependent variable and mediator were included as covariates in mediation models. Physical activity minutes and VLQ scores were z-score normalized to correct for significantly larger variances.

References

Knowles, J. E., Frederick, C., Whitworth, A., & Knowles, M. J. E. (2023). Package 'merTools'.

Rosseel, Y. (2012). lavaan: An R package for structural equation modeling. *Journal of statistical software*, 48, 1-36.

Selya, A. S., Rose, J. S., Dierker, L. C., Hedeker, D., & Mermelstein, R. J. (2012). A practical guide to calculating Cohen's f^2 , a measure of local effect size, from PROC MIXED. *Frontiers in Psychology*, 3, 111.

Van Buuren, S., & Groothuis-Oudshoorn, K. (2011). mice: Multivariate imputation by chained equations in R. *Journal of statistical software*, 45, 1-67.

Wing, R. R., Tate, D. F., Gorin, A. A., Raynor, H. A., & Fava, J. L. (2006). A self-regulation program for maintenance of weight loss. *New England Journal of Medicine*, 355(15), 1563-1571.

Zhang, Y. W. (2013). CPLM: compound Poisson linear models. *A vignette for R package cplm*. Available at <http://cran.r-project.org/web/packages/cplm>, 619, 621.

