Primary Aim (Efficacy of ABBT). Analyses will be conducted via linear mixed effects models for longitudinal data, which increase power by fully exploiting the strong correlation in treatment outcomes of interests (i.e., primarily, percent weight loss and secondarily, percent binge frequency reduction) across time. Patterned covariance matrices as implemented in SAS/STAT PROC MIXED V9.2 will be used to evaluate between group differences for percent weight loss and percent binge reduction across the study as a whole, and at each assessment post-baseline.²²⁵ Separate variance components will be used to capture therapist and participant-within-therapist variation. The within-subject covariance matrix will be assumed common across study arms, with an exponential variance function to deal with heteroscedasticity and a continuous-time AR(1) correlation matrix to accommodate residual autocorrelation over the unequal-size time intervals between follow-ups. Outcomes at all six time points will be estimated jointly for maximum statistical efficiency in the presence of intermittent missingness and loss to follow-up. The model will include random effects for subject and time (with higher-order effects if needed to capture nonlinear change), and fixed effects for treatment arm, time by treatment interaction, demographic information, and baseline values of weight, dietary intake and physical activity. Time-specific covariate-adjusted contrasts will be used to compare outcome between groups.

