Missing data. Our likelihood-based estimation methods remain unbiased when missingness is related to previously-observed outcomes as well as model covariates.²³⁶ If loss to follow-up is related to the missing outcome itself (an assumption that by its very nature cannot be tested empirically), we will use sensitivity analyses based on multiple imputation models²³⁷ to explore how robust our findings are with respect to a range of assumptions regarding missing data. We feel that these approaches are superior to alternatives (such as including only subjects with complete data or assigning a pre-specified score to the missing data) because these methods typically generate tests that are less powerful than the tests used assuming random censoring. We have experience with each of these approaches for handling non-ignorable non-response, and will analyze the data using several of these methods, which incorporate varying assumptions about the missing observations. To determine the extent to which the pattern of missing data might influence our findings, two approaches will be used. Compliance rates will be calculated for each participant. Participants with markedly low compliance rates (e.g., attendance at fewer than 3 assessments) will be considered for exclusion from analyses. Secondly, pattern mixture models^{169, 172, 174, 175} based on a random regression model (RRM)^{238, 239} will be used to examine the impact of missing data patterns on all variables. Subjects will be divided into groups based on their missing data pattern following the guidelines provided by Hedeker & Gibbons.²⁴⁰ The influence of missing data patterns on key variables will then be evaluated using RRM by comparing groups. If missing data patterns are found to be associated with key variables, this variable will be used as a covariate in subsequent analyses.

C11. Power Analyses

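### Missing primary-outcome weights are filled once on a fixed regain path; the SAP gives no reason for replacing the protocol's missing-data plan and lists no other analysis of weight beside it

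*SAP*

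**What the plan says.** Weight change is the primary outcome (Protocol C9) and is analysed as percent weight loss (C10, Primary Aim).

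**Protocol.** C10, Primary Aim: "Outcomes at all six time points will be estimated jointly for maximum statistical efficiency in the presence of intermittent missingness and loss to follow-up". C10, Missing data, relies on likelihood estimation, valid when missingness depends on earlier observed outcomes and covariates. Whether loss depends on the unseen weight itself is "an assumption that by its very nature cannot be tested empirically"; for that case "we will use sensitivity analyses based on multiple imputation models", over a range of assumptions. The same section adds pattern-mixture models. It ranks its approaches above complete-case analysis and above giving missing data a score fixed in advance. C11, Primary Aim, again counts on multiple imputation.

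**SAP.** For weight: "Single imputation was used to impute weight measurements using a return-to-baseline approach, with dropouts assumed to have regained 0.15lb per week", stopping at baseline weight. The support given is "consistent with assumptions used by other weight loss clinical trials", with one citation. For everything else: "Other missing variables were imputed using R" mice package. A mixed model for percent weight change follows. The one robustness check reported concerns another matter: "No differences in results were observed when treatment format delivery" was entered as a covariate. On summaries: "Descriptive statistics were generated for all variables at each assessment point by treatment condition". The SAP does not say whether these precede imputation or count missing weights.

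**The concern.** The mixed model remains, but it no longer handles the missing weights. They are set beforehand by a deterministic rule with one rate for both arms, and the model then takes them as measured. The result for the primary outcome therefore rests on a single assumption about unseen weights, of the kind that the protocol says the data cannot check. The analyses that the protocol planned around that assumption are not listed for weight.

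At stake is whether the comparison of ABBT with SBT depends on the rule. That turns on how many weights are missing in each arm and when. The documents report neither, so a reader cannot judge the direction or the size of the effect.

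**Working it through.** **1. The plan's own figures.** C11 requires 104 and allows up to 20% attrition: 104 / (1 − 0.20) = 130, as stated. That allows for 26 participants without data, 13 per arm if equal. The target is 3.5 points at d = 0.46, so SD = 3.5 / 0.46 = 7.6. At one visit with 65 per arm on complete data, SE = 7.6 × √(2/65) = 1.33 and power is 75% without covariates. The powers below should be compared with each other, not with the protocol's 80%, which also draws on covariates and repeated measures.

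**2. What the path adds.** Regain is 0.15 × weeks: 7.8 lb over 52 weeks (month 12 to 24), 11.7 lb over 78 weeks (month 6 to 24) and 13.65 lb over 91 weeks (month 3 to 24). At an assumed baseline of 240 lb these are 3.3%, 4.9% and 5.7%, against a target difference of 3.5 points.

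**3. Limiting case by hand.** Suppose that dropout is unrelated to weight and every dropout is back at baseline by month 24. With dropout p and mean loss m in each arm, the path estimate is

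(1 − p_ABBT) × m_ABBT − (1 − p_SBT) × m_SBT.

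Take m_SBT = 4.5 (assumed) and m_ABBT = 4.5 + 3.5 = 8.0, or 4.5 under no effect:
- 20%/20%: 0.8 × 8.0 − 0.8 × 4.5 = 2.8
- ABBT 30%, SBT 10%: 0.7 × 8.0 − 0.9 × 4.5 = 1.55
- ABBT 10%, SBT 30%: 0.9 × 8.0 − 0.7 × 4.5 = 4.05
- ABBT 10%, SBT 30%, no effect: (0.9 − 0.7) × 4.5 = 0.90

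These fix the directions. In practice not every dropout reaches the cap.

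**4. Simulation, missing at random.** Month 24, 65 per arm, SD 7.6, correlation 0.9 per visit step, baseline 240 lb (SD 40). Unless noted, dropout follows month 1, 3 or 6 and is likelier after smaller observed loss. The SAP does not say how a dropout last seen above baseline is filled; gains were carried forward. The path is analysed by a two-sample comparison. The likelihood column uses maximum likelihood with visit-specific means.

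| ABBT / SBT dropout | True difference | Path | Likelihood |
|---|---|---|---|
| 20% / 20% | 3.5 | 2.9, power 62% | 3.5, power 69% |
| 20% / 20%, only after month 12 | 3.5 | 3.4, power 73% | – |
| 30% / 10% | 3.5 | 2.1 | 3.5 |
| 10% / 30% | 3.5 | 3.8 | 3.5 |
| 10% / 30% | 0 | 0.55, false positives 7–8% | 0.0, 5% |
| 10% / 30%, SBT loss 9.8% | 0 | 1.1, false positives 14% | – |
| 15% / 25% | 0 | 0.29, false positives 5% | – |

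At 20%/20% with no effect, path false positives stay near 5%. Late dropout costs little: most late dropouts stop short of the cap, so much the same regain comes off both arms and the difference survives. With losses of 13.3% and 9.8% and dropout of 13–22% spread over later visits, the path gave about 3.1 to 3.4.

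**5. The reverse case.** If dropouts truly follow the path, the truth is 2.9 at 20%/20% and 2.1 at ABBT 30%, SBT 10%. Likelihood gives 3.5 both times, with 93% and 83% coverage.

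**6. Varying one common rate.** From 0.05 to 0.30 lb/week the path moves only from 2.98 to 2.87 at 20%/20%. Such a sweep never approaches 3.5, so it would not reveal the gap.

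**The case against.** The path has cited precedent, and a regain assumption is often taken as cautious. Much of the harm above needs a dropout imbalance that the documents do not show. They give only the 20% allowance (C11) and 82.6% retention at 12 months in an earlier trial (C1), neither by arm for this study. At 15%/25% false positives are nominal. At 10% dropout in both arms, with covariates assumed to explain 31% of the variance, power is 83% for the path against 85% for likelihood. C9 plans attrition and retention as feasibility measures, and C10 plans summaries by arm. The protocol's multiple-imputation sentence is conditional on loss depending on the missing outcome.

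Most of this stands as a limit on size, and none of it supplies the missing analyses. Precedent supports the path as one assumption; it does not explain replacing the planned method. The condition in the protocol is one that it calls untestable, and the section goes on to commit without condition to several methods under varying assumptions. Overall attrition is not a count of missing weights by arm and visit.

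A reader might infer more than the documents support:
- *That the SAP dropped the mixed model.* It did not; only the handling of missing weights changed.
- *That the alternative analyses were never run.* They are not listed; they may exist.
- *That the rule was chosen after seeing results.* The SAP is in the past tense, but no timing is given.
- *That the path favours ABBT, or that likelihood is the right answer.* Each depends on unreported dropout and unseen weights.

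**Conclusion.** The point holds as a departure from the protocol's missing-data plan for the primary outcome, with no reason or timing given and no observed-data, multiple-imputation or pattern-mixture analysis of weight listed. It should be fixed.

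The path cannot simply be called conservative. Under missing at random it shrinks a true difference when dropout is equal or higher in ABBT, and it can favour ABBT when SBT dropout is higher. If dropouts do regain, the observed-data estimate is the one that errs upward.

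The sizes are illustrative. They rest on assumed dropout rates and timing, assumed losses and a fixed SD, and they move outside any narrow range when these change. They come from single-visit stand-ins, not from the C10 model (random time effects, serial correlation, therapist components) or the SAP's quadratic-time model. They show that the conclusion could depend on the choice, not that it does.

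**What to change.** 1. Report the C10 mixed model on observed weights from all randomised participants beside the fixed-path result. Label which was pre-specified, and state why and when the method changed. The ground is pre-specification, not a claim that likelihood is superior.
2. Report missing weights by arm and visit, before imputation.
3. Carry out the protocol's sensitivity analysis for weight, by pattern-mixture models or by multiple imputation combined with Rubin's rules, with regain assumptions that may differ by arm. One common rate varied for both arms is not enough.

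The cost is a re-run on existing data and a few lines of text. The observed-data standard error is somewhat wider: at 20% dropout in the illustration, 1.42 against 1.29, about 10%. If dropouts did regain, the observed-data estimate alone would be too high (3.5 against 2.9), which is why the path result should stay beside it.

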A5. Behavioral weight loss interventions for BED are less effective than CBT at reducing binge eating and produce only modest weight loss.

Behavioral weight loss (BWL; which uses behavioral techniques to reduce caloric intake and increase physical activity⁶³) is the most effective behavioral treatment at producing weight loss in BED.⁵¹ BWL also improves binge eating, although not as well or consistently as the improvements observed in CBT.⁵¹ Although BWL is the most effective behavioral weight loss treatment to date for BED, weight loss remains, on average, modest. For example, [name] found that BED patients in a BWL program showed only a 2.1 mean percent BMI loss at 12-month follow-up.⁶⁴ Most trials to date have found that patients with BED experience poorer weight outcomes than obese peers without BED, although a number of studies have not demonstrated this relation, particularly when using samples of self-assessed binge eaters or sub-threshold BED cases.^{65, 66} These mixed findings may be related to methodological shortcomings (e.g., reliance on self-report questionnaires, inclusion of heterogeneous patients with sub-threshold levels of BED), and a lack of long-term follow-up data.^{51, 64, 66} Despite the inconsistencies observed in individual trials, a recent meta-analysis conducted by our team comparing BED patients with matched obese peers without BED demonstrated a clear impact of BED on weight loss in BWL, with obese BED samples losing significantly less weight (M=6.95kg) compared to obese peers without BED (M=13.51). The long-term outcomes for BWL

treatments in BED are especially poor, as patients with BED tend to re-gain lost weight more quickly than obese peers without BED⁶⁷⁻⁶⁹ and are more likely to drop out of treatment programs compared to obese peers without BED.⁶⁷⁻⁷⁰ Weight gain is often exacerbated by continued, or re-emergent, binge eating.⁶⁴

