C9. Assessments and Measures. Assessments will occur at the start of treatment (baseline), 1 month (midpoint 1), 3 months (midpoint 2), 6 months (midpoint 3), 12 months (post-treatment), and 24 months (1-year follow up). All outcome and process measures described below will be completed at each assessment. Acceptability will be assessed at post-treatment. All assessments will be completed onsite in Drexel University's Department of Psychology. Efforts will be made to schedule midpoint assessments directly after or directly before a treatment session to reduce participant travel burden (e.g. month 3 assessment will occur between sessions 12 and 13, with effort made to schedule participants right after session 12 or right before session 13 if possible). All assessments will be conducted by blind raters (graduate students who will be highly trained and closely supervised by [name]). Blind raters will receive training on standard procedures for collecting anthropometric data and administering all process measures described below. Raters will be required to pass a "mock" assessment with [name] and reach 100% agreement on eating disorder diagnosis and acceptable reliability (>.80) on EDE scoring before they will be cleared to conduct assessments.

Feasibility and Acceptability. Assessment of feasibility will include number of patients screened per month, % of eligible patients enrolled, treatment attrition (% of patients that prematurely terminate treatment), study retention (% of patients that complete all assessments), treatment adherence, and treatment fidelity. Acceptability will be assessed using the Feedback Questionnaire and Credibility/Expectancy Questionnaire¹⁹⁴ to gauge participant's attitudes and feelings toward the treatment.

Outcomes. The primary outcome measure for the study will be change in **weight**. Weight will be measured in street clothes without shoes using a standardized Secca® scale accurate to 0.1 kg. **Eating pathology** will be a secondary outcome measure and will be measured by The Eating Disorder Examination (EDE), a widely utilized, semi-structured interview for eating disorder symptoms.¹⁹⁵ Participant's EDE global scores and objective binge frequency will be the primary outcome measures for eating disorder pathology.

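### Dropouts' weight is assumed to regain, while binge frequency and EDE score go to mice with no stated shift, no reason for the difference and no test of relapse after dropout

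*SAP*

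**What the plan says.** The missing-data text in the opening paragraph of the SAP begins "Data were imputed via two methods to address missingness". The first method is for weight: single imputation, "with dropouts assumed to have regained 0.15lb per week up to their baseline weight", with an earlier weight-loss trial cited as precedent. The second covers all the rest: "Other missing variables were imputed using R" package mice. By implication that includes objective binge frequency, EDE global score and the mediators. The SAP does not state the predictors in the mice model, the number of imputations, how results were pooled, or any shift for participants who left. It describes no sensitivity analysis for missing data.

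The protocol (C9, Outcomes) makes weight change primary and eating pathology secondary. Of the latter it says: "Participant's EDE global scores and objective binge frequency will be the primary outcome measures for eating disorder pathology". Its Missing data paragraph in C10 made two commitments. If loss to follow-up depends on the unseen outcome, multiple-imputation sensitivity analyses would be used "to explore how robust our findings are with respect to a range of assumptions regarding missing data". Separately, and without that condition, pattern-mixture models would examine the effect of missing-data patterns for every variable. Section A5 links the two outcomes: "Weight gain is often exacerbated by continued, or re-emergent, binge eating".

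**The concern.** For the same person who leaves, the SAP assumes some loss of benefit on weight but states no such assumption for binge eating or EDE. The protocol's rationale makes it plausible that some leavers who regain weight also resume binge eating. The unshifted rule may therefore be too favourable to them, and the reader has no second analysis to show how much depends on it. Eating pathology is half of the trial's clinical question, so a claim of benefit there needs the same scrutiny as weight. There is a smaller consequence for mediation: where a mediator is itself missing, a regained weight may be paired with a mediator imputed under a different assumption.

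**Working it through.** **Inputs from the documents.** Attrition up to 20%, not split by arm (protocol C11, Primary Aim). Target difference of 4 binge episodes per 4 weeks (same section; no SD given). Weight regain of 0.15 lb per week (SAP). Assessments at months 0, 1, 3, 6, 12 and 24 (protocol C2).

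**The plan's own attrition figure.** 104 / (1 − 0.20) = 130, which matches the protocol's total sample size. The 20% is used below.

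**What the weight rule implies.** Assume a 230-lb participant who had lost 7% (16.1 lb) and left at month 6.
- By month 12: 0.15 × 26 = 3.9 lb, and 3.9 / 16.1 = 24% of the loss regained.
- By month 24: 0.15 × 78 = 11.7 lb, and 11.7 / 16.1 = 73% regained.

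For an assumed 250-lb participant with the mean losses of the earlier non-BED trial Mind Your Health II (9.8% = 24.5 lb; 13.3% = 33.25 lb), the month-24 figures are 11.7 / 24.5 = 48% and 11.7 / 33.25 = 35%. The rule is usually a partial regain, not a full return.

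**What a relapse assumption does to binge frequency.** Let A and S be the mean reductions in ABBT and SBT with no shift, dA and dS the dropout proportions, and k the share of improvement that leavers lose. Then

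contrast = A(1 − k·dA) − S(1 − k·dS).

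Equal dropout d reduces this to (A − S)(1 − k·d). With A − S = 4 and d = 0.20:

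| k | Contrast (episodes) |
|---|---|
| 0 (no shift) | 4.0 |
| 0.25 | 4 × 0.95 = 3.8 |
| 0.5 | 4 × 0.90 = 3.6 |
| 1 (full return) | 4 × 0.80 = 3.2 |

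A shift of the size in the 230-lb example (k = 0.24 to 0.73) gives 4 × 0.952 = 3.8 to 4 × 0.854 = 3.4. Each arm's own mean reduction falls by the factor 1 − k·d, so by one fifth at full return.

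Unequal dropout, full return (k = 1); reductions and dropout split are assumed:
- A = 12, S = 8, dropout 25% ABBT / 15% SBT: 12 × 0.75 − 8 × 0.85 = 9.0 − 6.8 = 2.2.
- A = 12, S = 8, dropout 15% / 25%: 12 × 0.85 − 8 × 0.75 = 10.2 − 6.0 = 4.2.
- A = 10, S = 6, dropout 15% / 25%: 8.5 − 4.5 = 4.0, unchanged.

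The contrast can shrink, stay or grow. Which one occurs depends on dropout by arm, which the documents do not give.

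**The case against.** Several stronger readings are tempting, and the documents do not support them.

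- A reader might infer that leavers are simply given retained participants' outcomes. The SAP does not say so. A mice model can use the leaver's own earlier binge and EDE values and, if weight was filled in first, the regained weight as well. That no shift was applied is the ordinary reading of an unqualified mice step, but it is an inference from silence.
- A reader might call the two assumptions incompatible. They are not. Section A3 treats overeating without loss of control as a separate route to weight gain. Section A4 describes CBT producing remission in up to 60% of patients with little or no weight loss. Section A5 says only that binge eating often worsens weight gain, and its remark on recurrence concerns very low calorie diets in many but not all studies.
- A reader might infer that all mediation results are distorted. The SAP uses mediator change to month 3 for post-treatment outcomes and to month 6 for follow-up. Someone who leaves after that visit can have an observed mediator. Only mediators missing at those visits are affected.

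It is also fair to say that no rule demands one missing-data method for all endpoints, that binge frequency and EDE are secondary, that the protocol's multiple-imputation sensitivity analyses were conditional, and that the protocol ranks assigning a pre-specified score as inferior. These points limit the concern. They do not remove it: the pattern-mixture commitment was unconditional and covered all variables, and the SAP neither describes it nor explains the different treatment.

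**Conclusion.** The point holds as an unexplained difference in assumptions and a missing robustness check, not as a contradiction or a demonstrated bias. As written, the SAP leaves the binge-frequency and EDE conclusions untested against relapse after dropout. At the protocol's 20% attrition, equal in both arms, a 4-episode contrast falls to 3.6 at half loss of improvement and 3.2 at full return. Under the assumed 25%/15% and 15%/25% splits, with reductions of 12 and 8, full return gives 2.2 or 4.2. These figures rest on assumed reductions, assumed dropout by arm and a common k in both arms, and they show scale only. The primary weight analysis is not affected by this point. It should be corrected before the eating-pathology result is called robust.

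**What to change.** In the SAP, state the mice model: predictors (including whether imputed weight is one), number of imputations and pooling. For binge frequency and EDE global score, add a delta-adjusted mice analysis in pattern-mixture form. It should run from no shift to full return to the participant's own baseline, and include a partial shift comparable with the weight rule. Allow the shift to differ by arm, and report dropout by arm. Present the results beside the mice result, and call the eating-pathology finding robust only if it holds across the range. In the mediation models, repeat the run under one common assumption for participants whose month-3 or month-6 mediator is missing.

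The cost is SAP wording and a re-run on existing data. The downside is a little more analysis work and a possibly less favourable result.
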